This study is a pilot trial investigating the feasibility of using activity monitoring data to adjust insulin pump therapy and prevent hypoglycemia. The study will enroll 20 patients 1-17 years old with type 1 diabetes mellitus on insulin pump therapy. Subjects will be provided with continuous glucose monitors (DexCom G4) and FitBit activity monitors. Study duration will be 3 to 4 months. During the course of the study patients will continue to receive routine care by their primary endocrinologist and DNE. Insulin dose adjustments unrelated to activity monitor data will continue to be at the discretion of the patient's primary diabetes team.

Activity level (steps and calories burned) will be uploaded over the web in a secure fashion to our central firewall-protected database on a daily basis while

CGM glucose values and insulin pump data will be collected once a week. Data from the activity monitor is automatically sent to a secure study team RedCap database once a day. This occurs by automatic, wireless syncing of the activity monitor with the patient/family's computer or smartphone. The activity monitor and activity monitor data is not associated with any personal health information. The activity monitor is only set up with a study identification number. Only study team members have access to the list of study identification numbers and associated patient information and this is stored in a secure computer a locked office. CGM and insulin pump data will be downloaded onto a patient or study team computer and then emailed to the study team once a week. Families will also have the option of coming to clinic once a week and having a study team member download the CGM and insulin pump data for them.

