instructed to calibrate the CGM a minimum of twice daily, before breakfast and before going to bed. Additional calibrations may be performed at the subject's discretion as in clinical practice. Sensors will be provided for replacement as needed (e.g. sensor falls off or fails internal quality checks included in the manufacture's product). Sensors may also be replaced at the subject's discretion should they observe the sensor is consistently not tracking blood glucose values as is standard practice. Subjects' CGM will be programmed with a low glucose alarm at 60 mg/dl. Subjects will also be requested to confirm episodes in which the sensor reports hypoglycemia with a capillary blood glucose meter measurement, and to treat hypoglycemia as per their home routine. At the completion of the study, CGMs devices will be collected.

Use of the FitBit Device. Combined with the initial training on CGM will be a short description of how the FitBit device works, and how the data obtained from the device will be used. Subjects will be encouraged not to make adjustments in insulin delivery based on the device readings, unless instructed by a research team member. At the completion of the study each subject will be allowed to keep FitBit monitors (valued at \$49.95 - \$99.95).

STUDY PROCEDURES:

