Insulin Pump Therapy: Participants will continue to use their own insulin pump and home blood glucose meter. All subjects will continue to receive routine care from their primary diabetes team. We propose to enact insulin dosing changes if we discover significant hyperglycemia and informing the diabetes providers of these changes." All other insulin dose changes unrelated to activity monitor data and energy expenditure estimates will be at the discretion of the primary team. We recognize that initial use of CGM may reveal previously undetected hypo- or hyperglycemia. Subjects and their families should discuss these findings with their primary diabetes team as they would for any other concerning blood glucose levels. If significant nocturnal hyperglycemia is detected, an increase in nighttime insulin basal rate will be recommended by the study team after being reviewed by the study endocrinologist. The dosing changes to address the hyperglycemia will be made by the study team directly in order to prevent delays in correction of the hyperglycemia as can occur if forced to wait for a response from the primary provider. Nevertheless, Tte recommended changes will also be sent as a powerchart message to the subject's primary diabetes care team and they will be given the option to opt out of the recommendation and contact the patient directly to address the discovered hyperglycemia. If the provider responds after the changes have been enacted then we will simply contact the family and ask them to resume their prior settings and discuss with their provider an alternative plan to treat the hyperglycemia.

Changes in Pump Therapy Based on Activity: During the first two to six weeks of the study, a baseline activity level will be established for each subject (average and standard deviation of first 14 days of available data). High activity

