days will be initially defined as any day where the activity is greater than one standard deviation above the mean. This definition, however, may need to be adjusted on a subject specific basis as it may vary due to physical fitness. Nadir glucose on increased activity days will be inputted into an adaptive basal algorithm. The algorithm is initialized with the subject's baseline insulin rate settings. Once the algorithm detects a need to modify the basal rate based on activity level, then an alternate basal profile will be recommended by the study physicians if deemed appropriate. The change will be made by the parent during one of the scheduled weekly phone calls or any other time of the week if needed. A study team member will walk the parent through the required steps to change insulin pump settings and confirm by verbal read back, screenshot or download that the pump settings are correct. Any changes to insulin pump therapy will be communicated to the subject's primary diabetes team via a note entered into the patient's BCH medical record.

Subject-Study Team communication: All subjects/families will be asked to contact the study team and perform a data download on a weekly basis. Families will be asked if they were compliant with CGM and activity monitor, if they had issues with blood glucose levels and if there were any intercurrent illnesses. Additionally, participants should contact a study team member if they experience any technical difficulties with their CGM or activity monitor, if they experience any nocturnal hypoglycemia (confirmed by home glucometer) or if they have concerns regarding a high activity day. Study team members will review daily activity data and call subject's families if an insulin dose change is recommended. A study team member will be available on page 24 hours a day.

Safety Monitoring: If CGM review reveals significant and recurrent hyperglycemia or activity-unrelated hypoglycemia, the subject's diabetes team will be alerted so that they may decide if changes to the subject's baseline insulin regimen are required. The study team may enact nighttime basal insulin dosing changes if significant nocturnal hyperglycemia is encountered while simultaneously alerting the patient's primary diabetes providers of these changes and giving them the option to change or refuse the recommendation.

d. **Definition of Primary and Secondary Outcomes/Endpoints**

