This is a pilot study to determine the feasibility of combining activity monitor data with CGM and pump data to make prospective recommendations to reduce basal insulin delivery following high activity days. There is no planned hypothesis for the pilot phase; however, planned comparisons for a larger study will be powered from the data obtained. The primary endpoint for the larger study will be a reduction in the incidence of nighttime hypoglycemia. Secondary outcomes will include the ability of activity data to predict nighttime nadir glucose.

Hypoglycemia will be defined as home meter glucose < 70 mg/dl for all subjects, CGM values below threshold for >30 minutes with no concomitant blood sugar reading (i.e. subject is sleeping at home and ignores the low glucose

alarm but the CGM is <70 for more than 30 minutes). Hypoglycemia episodes within one hour of each other will be considered as one event. Two hypoglycemic events with an intermittent blood glucose value above 70 mg/dL will be treated as a single event. Hypoglycemia and “use-of-supplemental- carbohydrate-to-prevent-hypoglycemia” will be treated identically.

5. Data Management and Statistical Analysis

One study folder, with IRB approved consent forms and case report forms (CRF), will be maintained for each subject recruited into the study. Sensor information, as provided by the manufacturer, will also be recorded on CRFs (identification numbers such as lot or serial together with expiration). Electronic data downloads for the insulin pump, containing a history of insulin delivery commands; glucose meter and glucose sensor, containing a record of all glucose values received and any alarms will be obtained weekly and the downloaded files copied to a password protected study computer in subdirectory labeled with the patient identification number. A copy of the spreadsheet used to screen blood glucose and activity data will also be placed in this directory.

a. Data Analysis Plan

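### After the study team raises overnight basal for nocturnal hyperglycemia, a CGM-only low is not a listed reason to call that team before its next weekly look at the CGM data, up to 7 nights later

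*Combined protocol and SAP*

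**What the plan says.** **The increase.** Under Insulin Pump Therapy in section 4c, if significant nocturnal hyperglycemia is detected, "an increase in nighttime insulin basal rate will be recommended by the study team", after review by the study endocrinologist. The study team makes the change itself, "in order to prevent delays in correction of the hyperglycemia as can occur if forced to wait for a response from the primary provider". The primary team is messaged and may opt out. If it answers after the change is in place, the family is asked to go back to the previous settings. Safety Monitoring, also in 4c, repeats the authority: "The study team may enact nighttime basal insulin dosing changes if significant nocturnal hyperglycemia is encountered".

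**The data flow.** Section 4a: "CGM glucose values and insulin pump data will be collected once a week". Subject-Study Team communication in 4c likewise sets family contact and downloads at weekly intervals. Only activity data are reviewed daily. No additional upload, call or check after an increase is described.

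**The reasons to call.** Apart from technical problems and concerns about a high activity day, families should contact the study team "if they experience any nocturnal hypoglycemia (confirmed by home glucometer").

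**The alarm and the event definition.** Under CGM Education in 4c, the "CGM will be programmed with a low glucose alarm at 60 mg/dl". Families are also asked to confirm sensor-reported lows by meter and to treat them by their home routine. The hypoglycemia definition in 4d uses 70 mg/dL and includes "CGM values below threshold for >30 minutes with no concomitant blood sugar reading", giving as its example a sleeping subject who does not respond to the alarm.

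**The primary team.** Insulin Pump Therapy says of highs or lows first revealed by CGM: "Subjects and their families should discuss these findings with their primary diabetes team".

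**The concern.** The protocol speeds up the dose increase on purpose but does not speed up the study team's look at what the increase did. The adverse response to too much overnight basal is a low in a sleeping child, and the trial enrols from age 1. Two kinds of low can pass without a meter value: one at 60 to 69 mg/dL, which is below the event threshold but does not reach the alarm setting, and one in which the alarm sounds and nobody wakes. The plan counts both as hypoglycemia if they last more than 30 minutes, yet neither is a listed reason to call the team that chose the rate. A rate that is too high could then run for several nights before that team sees its effect.

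The activity-based alternate rates matter less here. They are reductions, so the response that goes unseen is mainly hyperglycemia or too small a reduction.

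**Working it through.** The plan gives no figure of its own on this point, so there is none to reproduce. The check sets the rules side by side and then counts nights.

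**Which lows reach the study team before the download**

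| Overnight event | Alarm at 60 mg/dL | Meter value | Hypoglycemia under 4d | Listed reason to call |
|---|---|---|---|---|
| Low seen, meter below 70 | possibly | yes | yes | yes |
| CGM 60–69 for >30 min, nobody looks | no | no | yes | no |
| CGM reaches the alarm level, alarm slept through, <70 for >30 min | yes | no | yes | no |

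The last two rows are the gap. A meter check the next morning cannot confirm a low that has already ended.

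**How long the study team waits for its first look**

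Input: weekly collection (section 4a), assumed on time. If the increase is made d days after a download, nights to the next download = 7 − d, for d = 0 to 6.

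- Range: 1 to 7 nights.
- Mean if the day is random: (7+6+5+4+3+2+1)/7 = 28/7 = 4.0 nights.

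The documents do not say on which day increases are made. Hyperglycemia is probably found at a download, which would put increases near the 7-night end, but that is inference.

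**How long a low waits to be seen in the 7-night case**

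For a low on night k, wait = (night of the next look) − k. The means weight the seven nights equally.

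| Study-team looks after night | Wait for a low on nights 1 to 7 | Mean | Maximum | Longest unseen run |
|---|---|---|---|---|
| 7 (current plan) | 6, 5, 4, 3, 2, 1, 0 | 21/7 = 3.0 | 6 | 7 nights |
| 3 and 7 (one upload) | 2, 1, 0, 3, 2, 1, 0 | 9/7 = 1.3 | 3 | 4 nights (4 to 7) |

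With a morning trace check and call, a CGM-only low is reported the next morning whichever night it falls on, provided the check is done. The upload row shows the upload acting alone; on top of the call rule it serves only as a backup for missed checks.

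**Burden**

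An upload after night 3 is needed only when the download is more than 3 nights away (d = 0 to 3), so at most one per increase. The number of increases is not given. At an assumed 1 to 3 per child in 20 children, the ceiling is 1 × 20 = 20 to 3 × 20 = 60 uploads, beside 12 × 20 = 240 to 16 × 20 = 320 weekly downloads.

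**The case against.** The strongest reply is that detection and treatment do not depend on the weekly download. The CGM alarms in real time. The request to confirm sensor lows by meter is not limited to alarmed values, so a parent who sees 65 mg/dL is covered by it, and a meter reading below 70 is then a listed reason to call. A team member can be paged at any hour, the weekly contact asks about glucose problems, and the contact list does not forbid other calls. The increase itself has endocrinologist review behind it and a primary team that can refuse or reverse it. All of this stands and confines the gap to lows nobody sees at the time. A reader might infer that lows could go undetected or untreated for a week; the documents do not support that.

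A reader might also infer that the primary team would be slow to help. The delay named in section 4c concerns that team's reply to a study-team message about hyperglycemia. It says nothing about how fast the team answers a family reporting a low. What can be said is that this route leads to a different team from the one that set the rate.

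Requiring a meter value is also a defensible choice. Section 2 notes doubts about CGM accuracy and false alarms, and section 4c bars dosing from sensor values. This is a good reason to keep the meter condition in general and to relax it only for a short period, for review only.

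None of this gives the study team an earlier look after its own increase. The CGM-review provision under Safety Monitoring uses the same weekly data.

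**Conclusion.** The point holds as a gap in study-team review. After a study-team overnight increase, the next scheduled look at CGM comes 1 to 7 nights later, and a CGM-only low in that time is hypoglycemia by the plan's own definition without being a listed reason to call. In the 7-night case the wait to be seen averages 3.0 nights and is at most 6. These figures rest on on-time downloads, and the mean also on a low being equally likely on each night.

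A reader might want a probability that a child has such a low, or might read a shorter unseen run as a lower risk. Neither is supported. The documents give no nightly rate of lows after an increase, and an earlier look changes risk only if it leads to a dose change. The size of the problem is therefore stated in nights alone.

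For a 20-child pilot with the other safeguards in place, this is a cheap improvement of minor weight.

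**What to change.** In section 4c, under Insulin Pump Therapy and Subject-Study Team communication, add a rule that runs from any study-team overnight basal increase until the next weekly download. Families look at the overnight CGM trace each morning and call the study team for CGM below 70 mg/dL for more than 30 minutes, even without a meter reading. The call prompts review only; dose decisions stay with the study physician. The meter-confirmed trigger stays as it is at all other times.

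As an optional backup for missed checks, ask for one home CGM and pump upload after about night 3, unless the weekly download is due sooner.

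The cost is up to 7 morning checks and at most one extra upload per increase, plus some calls for false sensor lows, whose number the documents do not allow one to estimate. If the optional upload is adopted, families who download only in clinic would need the study-provided computer that section 4c already offers.

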Adjusting Insulin Delivery to Activity (AIDA):

Use of Activity Data to Adjust Insulin Pump Therapy for Children with Type 1 Diabetes

AIDA Investigation Protocol

Investigators:

[name]
[name]
[name]
[name]

NCT: 022994479

Version Date: September 21, 2016

Summary/Abstract

Being diagnosed with type 1 diabetes at a young age places a lifelong burden on the child together with new challenges and responsibilities for the parents of that child. New technologies such as continuous glucose monitors (CGM) and high resolution insulin pumps with the ability to deliver the low basal rates required for very young children have reduced the burden, but the pumps need to be carefully configured with some of the setting needing to be subtly adjusted following exercise, which if performed later in the day has been shown to reduce the nighttime basal requirements. Many adults with type 1 diabetes (T1D) are able to intuitively make adjustments based on prior activity; however, parents of younger children may not even be aware of their child's activity levels while at day-care or school. Moreover, the amount and timing of the adjustments are not well defined and may be highly variable between subjects. The present study looks to assess the feasibility of combining new generation activity monitors (FitBit or similar), with data obtained from CGM and insulin pump records to improve insulin dose adjustments and prevent hypoglycemia in the pediatric population.

Abbreviations: SAP – sensor augmented pump therapy; CGM – continuous glucose monitor; T1D – type 1 diabetes; TDD – total daily dose;

1. Specific Aim:

To determine the feasibility of using activity monitor data to predict the need to make temporary insulin pump dose adjustments to prevent nighttime hypoglycemia.

2. Background and significance

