The initial 2 weeks of a subject's enrollment in the study will be used to establish his or her baseline activity level and no changes to the insulin regimen will be made based on the activity monitor data. During weeks 3-6 to 12-16, activity data will be reviewed daily and an alternate basal insulin rate will be recommended on days considered to be increased activity days. We will use an adaptive algorithm to help guide suggested nighttime insulin basal rate changes. All recommendations will be reviewed and approved by a study physician prior to implementation. The alternate rate will be derived using the subject's usual care pump settings as an initial starting point from which to make incremental changes in the 3 hour interval leading up to the hypoglycemic event. Target will be the overnight nadir obtained with usual care settings. Residual error (CGM-target) will be used to assess the validity of using the 3 hour window prior to the event to effect lower basal. The patient's primary diabetes team will be informed about the recommended nighttime basal insulin dose change and this will be documented in the patient's medical record in powerchart. The primary diabetes team will not give recommendations regarding nighttime insulin rate dose changes based on activity monitor data; however, they will continue to guide all other aspects of the patient's diabetes management.

b. Patient Selection and Inclusion/Exclusion Criteria

Subjects will be recruited from the outpatient endocrinology clinic based on physician recommendation and approval to approach at Boston Children's Hospital (BCH) as well as through public notice. 20 subjects will be recruited in two different age designations.

Inclusion Criteria:

- Age: 1 to 17 years old
- Type 1 diabetes (as clinically diagnosed by outpatient endocrinologist).
- Treated with insulin pump therapy for greater than or equal 3 months

- Families will need to have access to Wi-Fi and a compatible smartphone in order for the data from the activity monitor and other devices to be transmitted to the research team

Exclusion Criteria:

- Current glucocorticoid use or other medication known to affect insulin action at investigator's discretion.
- Hospitalization within the last month

c. **Description of Study Treatments and Procedures**

RECRUITMENT, SCREENING AND CONSENT:

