Subject will be recruited from the Boston Children's Hospital Endocrinology Clinic. We will screen the clinic schedule for eligible candidates. Eligibility will be assessed.. Primary providers will be approached regarding eligible patients and asked to introduce the research team at the time of the clinic visit. Consent, and assent for patients older than 7 years old, will be obtained during the patient's clinic visit. Additionally, we will contact by email all diabetes providers to inform them of our study and ask them to give interested families the approved study information sheet, which has study team contact information (email and phone number is given on the sheet). For interested subjects who contact us but do not have an upcoming clinic visit, consent will be obtained at the Training and Education visit.

TRAINING AND EDUCATION:

After initial recruitment discussions, subjects will be requested to come to the Endocrine outpatient clinic located at [name]. A trained research team member will teach during a 1-2 hour session use of the continuous glucose monitor and the activity monitor. Families will also be instructed how and when to upload data from the insulin pump, CGM and activity monitor. Families will have the choice to use their own computers, use a study team-provided computer or come to clinic in order to upload data once a week. Activity monitor data will be uploaded automatically on a daily basis when subjects are near a Wi-Fi connection.

CGM Education: A trained research team member (nurse or physician) will provide education surrounding the use of the CGM, including technical aspects related to insertion and removal of the device, alarms, and calibration. Subjects will be informed that sensor values are not to be used to dose insulin and that prior to administering insulin they should obtain a blood glucose value from their standard meter (i.e., follow normal routines). Subjects will be

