Data analysis will begin by calculating the baseline (average and standard deviation) activity level for each subject during the first two to six weeks. High activity days will be defined as any day where the activity is greater than one standard deviation above the mean. Correlations will be performed to assess if there is relationship between daytime activity (8- am to 9 pm) and nighttime nadir blood glucose level (continuous). Nadir glucose will also be categorized as hypo- or no-hypo (binary), with a binary logistic regression model used to assess the significance of daytime activity, insulin dosing, and carbohydrate intake, as independent factors increasing the risk of hypoglycemia. Analysis will proceed with generalized estimating equations (not powered but in preparation of the larger study to be conducted). Characteristics of the nighttime glucose profile (nadir glucose, time in target, time below target) will be calculated weekly, with mean and 95% confidence plotted by week. In the event usual-care pump settings are adjusted during the course of the study, the average nighttime glucose values observed for the week following the most recent adjustment will be compared to average values obtained during the final week (assures improvements are due to the availability of the FitBit data rather than the CGM data). Chi2 analysis will be used to assess differences in the incidence of hypoglycemia. Statistical analyses will be performed both as intention to treat and per protocol. The intention to treat analysis will include all data; per protocol analysis will exclude cases in which the subject does not comply with recommendations of the study team or does not complete all 12 weeks of the study. The algorithm will be considered feasible if all data can be assembled, and recommendations deemed reasonable (accepted) in a majority of cases.

Statistical Power and Sample Considerations

This is a feasibility study and therefore is not powered; however, the choice of 10 subjects with any one group is generally considered acceptable for feasibility/pilot-studies and should provide sufficient data to power a larger study.

Study Organization

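### The aim is prospective, but the plan neither sets nor records when activity flags arrive relative to the night concerned, so the feasibility rule can be met by flags that come too late

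*Combined protocol and SAP*

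**What the plan says.** - **Aim.** Section 1 asks whether activity data can "predict the need to make temporary insulin pump dose adjustments to prevent nighttime hypoglycemia". Section 4.d describes the recommendations as prospective, and the background (Section 2) names a patient alert tool as the long-term goal.
- **Data transfer.** Section 4.a: "Data from the activity monitor is automatically sent to a secure study team RedCap database once a day". Section 4.c, Training and Education: "Activity monitor data will be uploaded automatically on a daily basis when subjects are near a Wi-Fi connection". Neither gives a time of day. CGM and pump data come in weekly (Section 4.a).
- **Review and approval.** Section 4.a: "activity data will be reviewed daily and an alternate basal insulin rate will be recommended on days considered to be increased activity days", and "All recommendations will be reviewed and approved by a study physician prior to implementation".
- **Pump change.** Section 4.c, Changes in Pump Therapy Based on Activity: "The change will be made by the parent during one of the scheduled weekly phone calls or any other time of the week if needed". The communication paragraph that follows adds that staff look at activity daily, call families when they recommend a change, and can be paged at any hour.
- **Family action.** Section 4.c, on the FitBit device, encourages families not to adjust insulin from its readings unless the research team instructs them to.
- **Analysis.** Section 5.a relates activity from 8 am to 9 pm to the night's lowest glucose.
- **Feasibility.** Section 5.a: "The algorithm will be considered feasible if all data can be assembled", with the second condition that recommendations are judged reasonable and accepted in more than half of cases.

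**The concern.** A flag about tonight is useful for tonight only if it reaches the family before the night begins. Between the child's activity and a changed pump setting lie five steps: transfer, review, physician approval, contact and the change itself. The plan gives none of them a deadline relative to the night and does not say that their times will be kept. Neither limb of the feasibility rule mentions time.

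Two conclusions of the pilot are exposed. First, it could declare the approach feasible without knowing how many flags could have been used. Second, the activity-nadir association would rest on a complete daytime record that may not have existed in the database when the decision had to be made. The Summary says that exercise later in the day is what lowers night-time basal need, so the hours most likely to be missing from an early transfer are ones the protocol itself regards as informative. The pilot is meant to supply the figures that power the larger study (Section 4.d), so an optimistic association would carry forward.

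**Working it through.** The plan states no figure on timing, so there is none to reproduce. The numbers below are illustrations under stated assumptions.

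**1. The steps side by side**

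| Step | Frequency stated | Deadline before the night | Time recorded |
|---|---|---|---|
| Activity transfer (4.a, 4.c) | once a day, near Wi-Fi | none | not stated |
| Review (4.a, 4.c) | daily | none | not stated |
| Physician approval (4.a) | before implementation | none | not stated |
| Family contact and pump change (4.c) | weekly call or any other time | none | not stated |
| Feasibility rule (5.a) | – | no timing condition | – |

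**2. Time available.** Section 5.a gives the night no clock start. The only basal window with clock times is midnight to 3 am, in the simulation of Section 3. Taking midnight as the start, 24 − 21 = 3 hours separate the end of the analysed activity window from the night, and fewer if the child is already asleep.

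**3. Transfers between 9 pm and midnight.** Assume one transfer a day at a time uniform between hour *a* and 24. The share with the full window in hand before midnight is 3/(24 − *a*).

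**4. Mean share of the 13-hour window on file by midnight.** Assume also that activity is spread evenly. For *a* between 8 and 21 the share is [(21 − *a*) × ½((*a* − 8)/13 + 1) + 3]/(24 − *a*). For *a* = 0 it is (13 × ½ + 3)/24.

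| Transfer uniform from | Full window before midnight | Mean share of window on file |
|---|---|---|
| 0:00 | 3/24 = 12.5% | 9.5/24 = 40% |
| 3 pm | 3/9 = 33% | (6 × 0.769 + 3)/9 = 85% |
| 6 pm | 3/6 = 50% | (3 × 0.885 + 3)/6 = 94% |
| 9 pm | 3/3 = 100% | 100% |

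The spread shows that the answer depends on a quantity the plan does not collect.

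**5. The feasibility rule with and without timing.** Let *A* be the share of recommendations accepted and *s* the share in time. The acceptance limb as written needs *A* > 0.5, whatever *s* is. If a recommendation had to be both accepted and in time, and the two were independent, the condition would be *A* × *s* > 0.5. With an assumed *A* = 0.80:

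- *s* = 0: 0%
- *s* = 0.125: 10%
- *s* = 0.50: 40%
- *s* = 1: 80%

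A majority would need *s* > 0.5/0.8 = 62.5%. The acceptance limb as written is satisfied in all four cases.

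**6. Number of nights at issue.** A high-activity day exceeds the child's own mean by more than one SD. If daily activity were normal and the baseline held, 15.9% of days would qualify. The activity-guided period could run from as little as weeks 7–12 (42 days) to weeks 3–16 (98 days), giving 6.7 to 15.5 days per child, or about 133 to 311 in 20 children. That is enough to estimate a timely share, provided the interval allows for clustering within child.

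**The case against.** The strongest defence is that the plan already has a same-day route. Staff look at activity daily, phone families when a change is recommended and can be paged around the clock. A reader might infer that pump changes wait for the weekly call. The text does not support this, because it allows a change at any other time of the week. Nor do Sections 4.a and 4.c clearly contradict each other on nightly against weekly timing. They simply do not say when, or by whom, an alternate profile is put into use on a particular night.

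A second defence concerns the mechanism. The alternate profile is built from the lowest glucose on earlier high-activity nights, so deriving it needs no same-evening transfer. This stands: same-day timing matters for using the profile, not for deriving it. Families may also raise a high-activity day themselves, and if a relationship is found the physician discusses recognising such days without relying on the device alone (Section 3).

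Third, the illustrative shares are not evidence about this trial. Transfer is automatic, families are taught when to upload, and the 8 am to 9 pm window is stated only for the correlation analysis. A running count can pass the one-SD threshold well before 9 pm, so a valid flag need not wait for the full record. All of this stands, and the percentages should be read only as a range.

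Fourth, the feasibility rule asks for more than data assembly, since recommendations must also be accepted in most cases. That is correct, but acceptance is not defined in terms of time, so the gap remains.

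**Conclusion.** The point holds as one of measurement. The aim is prospective, no step is timed relative to the night, the times are not planned to be recorded, and the Section 5.a rule can be met whatever share of flags came in time. The association based on the full daytime record can overstate what an evening alert could achieve.

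A reader might go further and infer that the data will come too late. The documents do not show that; they show only that lateness is neither excluded nor measured. The size is therefore unknown. Under assumed transfer times, the share arriving between 9 pm and midnight spans 12.5% to 100%, and those figures rest on a midnight start of the night and on waiting for the complete window. For an unpowered pilot with no planned hypothesis this is not a fatal flaw, but feasibility is the pilot's purpose and the remedy is cheap, so the change should be made.

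**What to change.** 1. For each child-day, store time stamps for data arrival, flag, physician approval and family contact.
2. Add to the feasibility criterion in Section 5.a the share of high-activity days that were flagged and communicated before the night concerned, with a confidence interval clustered by subject. State the clock start of the night used for this count.
3. Use the insulin delivery history already in the weekly pump download (Section 5) to classify which basal profile ran each night. This needs no new data.
4. Repeat the activity-nadir analysis using only activity received by a pre-stated evening cut-off, and present it as the estimate relevant to prospective use. Keep the full-window analysis alongside it.
5. The sponsor should clarify Sections 4.a and 4.c on when the alternate profile is applied. No clinical rule is proposed here; the cut-off in item 4 is for analysis only.

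The cost is a small logging burden for the study team, an amended feasibility sentence and one repeated analysis. The downside is that the reported feasibility figure may be less favourable.
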